6.0 ASSESSMENTS

6.1 Clinical Assessments

The logistics of the study are summarized in the table, 15.1.8. Patients will be evaluated in the clinic by an investigator before each treatment cycle. Before each cycle of therapy, patients will have routine and correlative science labs performed along with a history and physical examination. These data will be recorded on a form (15.1.4 Clinical Evaluation). An adverse event form will also be completed at each of these evaluations by the study nurse-coordinator (see below). Patients will have staging performed with CT/PET or CT (CAP) after every complete course of treatment (2 complete cycles of HD IL-2 plus 4 weeks of rest plus 3 weeks of oral temozolomide plus 2 weeks of rest prior to reimaging = 1 complete course = approximately 12 weeks). Patients with measurable skin and/or subcutaneous lesions would have 2-dimensional measurements performed using a ruler after each complete course of therapy. They will also have an autoimmune panel drawn after each complete cycle. The autoimmune panel will include an ESR, CRP, ANA, RF, and TSH. Patients with known brain metastases will have repeat MRI of the head after each course. Patients with or without known brain metastases can get repeat MRI at any time should they develop neurologic symptoms as determined by the investigator. Response will be by modified RECIST criteria 1.1 and will employ the following definitions of response:

CR – complete response - no evidence of disease, 100% reduction in the volume of disease

PR – partial response - $\geq 50\%$ but $< 100\%$ reduction in volume of disease

MR – minor response - $\geq 25\%$ but $< 50\%$ reduction in volume of disease

SD – stable disease - $< 25\%$ increase in volume of disease to $< 25\%$ reduction in volume of disease

PD – progressive disease - $\geq 25\%$ increase in volume of disease

The final response will be the best response observed during the course of treatment while on study

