8.0 DATA ANALYSIS AND STATISTICAL METHOD

8.1 Sample Size Determination

The study will employ a Simon 2-stage optimal design with the following specifications: $p_0 = 0.05$, $p_1 = 0.20$, $\alpha = 0.10$, $\beta = 0.10$, where p_0 is the ineffective response rate, p_1 is the effective response rate, α is the false positive rate, and β is the false negative rate. With these specifications, a 2-stage Simon optimal design, which minimizes the expected sample size given an ineffective response rate, will enroll a total of 37 patients with 12 during stage 1 and 25 during stage 2. If there is no response among the first 12 patients, then the drug is considered ineffective and the enrollment will be stopped. Otherwise, the study will proceed to stage 2. The drug will be considered effective if there are at least 4 responses by the completion of the trial.

The design will assure good statistical power with respect to differentiating response rates of 5% and 20% (12). Three additional patients will be enrolled to allow for dropouts to a total of 40.

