8.2 Efficacy Determination

Efficacy analysis will be performed on the intention-to-treat set, which comprises of all patients enrolled in the trial. Patients must have completed at least one complete course (2 cycles) to be considered for response assessment. Patients receiving less than one course will be considered drop-outs from the study in terms of response. Patients who do complete at least one course of treatment will be classified as responders or non-responders. The overall response rate, which is the proportion of the responses among patients in the intention-to-treat set who have completed at least one complete course, will be obtained. In addition, a 95% confidence interval for the overall response rate will be constructed. Responses will be recorded after each course of therapy and will be tabulated as complete response, partial response, minor response, stable disease or progressive disease. Only PR and CR will be included in the numerator of the analysis for overall response but all responses will be recorded. The time to progression (TTP) in months for each patient will be recorded to ascertain the durability of the responses. Waterfall plots for a continuous assessment of response will also be generated. Correlative science results will be studied by non-parametric methods for differences in a given individual over time and between individuals.

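### A CR or PR seen on a single scan counts in full toward the four-response rule, and the plan does not say whether its 5% and 20% rates are confirmed rates

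*Combined protocol and SAP*

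**What the plan says.** Section 6.1 introduces its own categories: "Response will be by modified RECIST criteria 1.1 and will employ the following definitions of response". Each category is a percentage change in disease volume, and PR starts at a 50% reduction. The section then closes with: "The final response will be the best response observed during the course of treatment while on study".

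Section 8.2 defines the numerator: "Only PR and CR will be included in the numerator of the analysis for overall response but all responses will be recorded". Section 8.1 sets the decision: "The drug will be considered effective if there are at least 4 responses by the completion of the trial". The stage 1 rule, also in 8.1, is: "If there is no response among the first 12 patients, then the drug is considered ineffective and the enrollment will be stopped".

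No repeat scan, minimum interval or minimum duration appears in sections 3.0, 5.3, 6.1, 8.1 or 8.2, or in the time and events schedule. Imaging takes place once per course, about every 12 weeks, for at most four courses.

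**The concern.** Under the best-observed rule, a later scan cannot remove a response once it has been recorded. A PR after course 1 followed by PD after course 2 has the same weight in the verdict as a lasting response.

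The verdict rests on a small count: 3 of 37 (8.1%) fails and 4 of 37 (10.8%) succeeds. The trial is single-arm and open label, and the document describes no blinded or independent reading of images. One borderline or short-lived PR can therefore decide the result. Time to progression is recorded, but it does not enter the rule.

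**Working it through.** **Inputs.** From section 8.1: p0 = 0.05, p1 = 0.20, alpha = beta = 0.10, 12 patients in stage 1 and 25 in stage 2, stop at 0 of 12, effective at 4 or more of 37. Assumed, because the document gives no figure: the added rate of transient or misread responses, and the share of responses that fail confirmation.

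**Formula.** Take every way of reaching 4 of 37 and remove those with no response in the first 12. With response probability p:

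P(declare effective) = P(Bin(37, p) ≥ 4) − (1 − p)^12 × P(Bin(25, p) ≥ 4)

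The last digit below may differ by one through rounding.

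**The plan's own design.**
- p = 0.05: 0.1119 − 0.5404 × 0.0341 = 0.0935.
- p = 0.20: 0.9550 − 0.0687 × 0.7660 = 0.9024.

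Both meet the stated limits. A search over two-stage designs also returns 12, 37 and a cut-off of 4 as the optimal design, so the sample size is right for its inputs.

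**How close the decision is.** At p = 0.05, the chance of passing stage 1 and ending on exactly 3 responses is 0.120. In those trials one extra reading reverses the verdict.

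**Added responses, if 5% is a true or confirmed rate.**

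| Added points (assumed) | Observed rate | Calculation | P(declare effective) |
|---|---|---|---|
| 0 | 0.05 | 0.1119 − 0.5404 × 0.0341 | 0.094 |
| 1 | 0.06 | 0.1797 − 0.4759 × 0.0598 | 0.151 |
| 2 | 0.07 | 0.2584 − 0.4186 × 0.0936 | 0.219 |
| 3 | 0.08 | 0.3433 − 0.3677 × 0.1351 | 0.294 |

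A second model applies a false-reading chance f to true non-responders only, so p = 0.05 + 0.95f. For f = 1%, 2% and 3%, p is 0.0595, 0.069 and 0.0785, and the results are 0.148, 0.212 and 0.282. The conclusion is the same.

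**Power under the fix, if 20% was an unconfirmed rate.** The confirmed rate is 0.20 × (1 − share failing). If stage 1 stays on observed responses, the stage 1 term remains 0.80^12 = 0.0687.

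| Share failing (assumed) | Confirmed rate | Stage 1 on observed responses | Stage 1 also confirmed |
|---|---|---|---|
| 5% | 0.19 | 0.9397 − 0.0687 × 0.7266 = 0.890 | 0.882 |
| 10% | 0.18 | 0.9201 − 0.0687 × 0.6829 = 0.873 | 0.857 |
| 20% | 0.16 | 0.8644 − 0.0687 × 0.5837 = 0.824 | 0.792 |

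**Type I error under the fix.** Suppose the confirmed rate is 5%, and unconfirmed readings of 1, 2 or 3 points help only to pass stage 1. The formula becomes 0.1119 − (0.95 − added)^12 × 0.0341. This gives 0.1119 − 0.4759 × 0.0341 = 0.096, 0.1119 − 0.4186 × 0.0341 = 0.098, and 0.1119 − 0.3677 × 0.0341 = 0.099. All stay below 0.10. The ceiling, if stage 1 never stopped the trial, is 0.112.

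**The case against.** The strongest objection is that alpha may not be inflated at all. Section 8.1 describes p0 only as the ineffective response rate. If that 5% was scored as best observed response, false and brief readings are already inside it. The historical rates in sections 1.3 and 3.0 are not labelled confirmed or unconfirmed. This objection stands, and it makes the inflation figures conditional.

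A reader might also infer three stronger points that the document does not support:
- **That reading error can only help.** A true PR can be read as MR or SD, and a patient read as PD after course 1 leaves the study with no later scan to correct it.
- **That every patient has four chances to respond.** PD ends treatment, and SD after course 1 allows one more course at most. Only patients in MR or PR can reach four courses, and those in PR are already counted.
- **That durability is ignored.** Duration of response is part of the second primary objective. Responses are tabulated after each course, and time to progression is recorded. A short response would be visible, though not in the verdict.

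In the other direction, one might say that citing RECIST 1.1 supplies confirmation. The criteria are called modified, and the section substitutes its own definitions and best-observed rule. A confirmation requirement has to be written to apply.

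Finally, the next scan follows another full course, so confirmation there tests persistence over about 12 weeks as well as reading accuracy. That changes the endpoint, which is why p0 and p1 must be restated with it.

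**Conclusion.** The gap is real and should be closed. An unconfirmed CR or PR is final, and the verdict can turn on one such reading.

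The rise from 0.094 to 0.151, 0.219 or 0.294 rests on two assumptions: that p0 = 0.05 refers to true or confirmed responses, and that 1 to 3 points of transient or misread responses occur. A reader might conclude that the trial's false positive rate is known to exceed 0.10. The document does not support that, because it defines neither the basis of p0 nor a misreading rate. Nor is this a sample-size error: the design reproduces exactly.

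**What to change.** Amend sections 6.1, 8.1 and 8.2 as follows.

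1. Base the at-least-4 verdict on CR or PR that is still at least PR at the next post-course scan.
2. State that p0 and p1 are confirmed rates.
3. Leave the stage 1 continuation rule on observed CR or PR, so that accrual does not wait for a second scan. Section 3.0 also lets an MR count at stage 1, whereas 8.2 excludes it; align the two.
4. Count a responder with no later scan (first response after course 4, or early departure) as unconfirmed, unless a follow-up scan within a stated window shows at least PR. Section 5.6 offers only record review, generally every 6 months or less, so the window must be written down.
5. Report the confirmed and unconfirmed rates side by side, and say whether the verdict is the same under both.

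**Cost.** This is mainly a change of wording. Under sections 5.3 and 6.1, most responders already receive another course and another scan. The sample size and cut-off do not change. The final verdict waits about 12 weeks for the last responders. If 20% was meant as a confirmed rate, there is no loss of power. If it was unconfirmed, power falls to about 0.89, 0.87 or 0.82 when 5%, 10% or 20% of responses fail confirmation. Requiring confirmation at stage 1 as well would lower these to 0.88, 0.86 or 0.79.

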6.2 Toxicity Assessments

Patients will have standard toxicity assessments performed before each cycle. These data will be recorded on a form. Safety outcomes will be based on observed or reported adverse events (AEs).

Other safety data will include other AEs or SAEs, as defined below, including abnormal results of objective tests that resulted in change in study drug dosage or discontinuation or clinically significant changes in physical examination findings unrelated to disease progression. Deaths will be reported immediately as SAEs, and autopsies requested.

6.2.1 Data Safety Monitoring Board

The Penn State Hershey Cancer Institute Data and Safety Monitoring Board (PSHCI DSMB) will serve as the independent board for data and safety review. The principal investigator (PI) will continuously monitor study progress for safety and will hold monthly meetings with the Disease Center Personnel to review overall conduct and progress of this study. During these meetings, accrual and all adverse events/safety issues will be discussed. The PI will provide the PSHCI DSMC annual safety and monitoring reports including the number of subjects enrolled, SAE assessments, information on any protocol deviations and breaches of confidentiality. Summary of all adverse events will be reported to the IRB annually; unexpected adverse events will be reported as they arise as well as any significant literature reporting developments that may affect the safety of participants in this study. Serious and unexpected adverse events will also be reported to PSHCI DMSB simultaneously with the IRB reporting. The PI will be responsible for ensuring the proper conduct of the study with regard to protocol adherence and the validity of the data recorded on case report forms. Reports from the PSHCI DSMB will be sent to the IRB at least annually.

6.2.2 Correlative Science Testing

Patients would have 50 ml of blood drawn for correlative science studies at baseline, 24-72 hours after the last dose of IL-2 for each cycle, the day patient starts temozolomide (-2/+0 days), and at the end of each complete course of treatment. The tests are described in more detail in Appendix III. Studies would include FLOW cytometry for quantification of T-cell subsets including T-reg cells, ELIspot for cytokine production (IL-2, TNF, IL-6, IL-12) and FLOW-based tetramer analysis for reactivity against common melanoma antigens such as MART and S100. Correlative science studies will be completed by [name]'s lab ([name]).

7.0 ADVERSE EVENT REPORTING

The investigator is responsible for the detection and documentation of events meeting the criteria and definition of an AE or SAE, as provided in this protocol. During the study when there is a safety evaluation, the investigator or site staff will be responsible for detecting, documenting and reporting AEs and SAEs. They will be submitted to the PSHCI DSMB and the HMC IRB for evaluation by those bodies.

This study will utilize the Common Terminology Criteria for Adverse Events (CTCAE) Version 4.0 for grading of all adverse events.

Definition of an AE

Any untoward medical occurrence in a patient or clinical investigation subject, temporally associated with the use of a medicinal product, whether or not considered related to the medicinal product.

Note: An AE can therefore be any unfavorable and unintended sign (including an abnormal laboratory finding), symptom, or disease (new or exacerbated) temporally associated with the use of a medicinal product. For marketed medicinal products, this also includes failure to produce expected benefits (i.e. lack of efficacy), abuse or misuse.

Definition of a SAE

A serious adverse event is any untoward medical occurrence that, at any dose:

a. Results in death

b. Is life-threatening

NOTE: The term 'life-threatening' in the definition of 'serious' refers to an event in which the subject was at risk of death at the time of the event. It does not refer to an event, which hypothetically might have caused death, if it were more severe.

c. Requires hospitalization or prolongation of existing hospitalization

NOTE: In general, hospitalization signifies that the subject has been detained (usually involving at least an overnight stay) at the hospital or emergency ward for observation and/or treatment that would not have been appropriate in the physician's office or out-patient setting.

Complications that occur during hospitalization are AEs. If a complication prolongs hospitalization or fulfills any other serious criteria, the event is serious. When in doubt as to whether "hospitalization" occurred or was necessary, the AE should be considered serious.

Hospitalization for elective treatment of a pre-existing condition that did not worsen from baseline is not considered an AE.

d. Results in disability/incapacity, or

NOTE: The term disability means a substantial disruption of a person's ability to conduct normal life functions. This definition is not intended to include experiences of relatively minor medical significance such as uncomplicated headache, nausea, vomiting, diarrhea, influenza, and accidental trauma (e.g. sprained ankle) which may interfere or prevent everyday life functions but do not constitute a substantial disruption.

e. Is a congenital anomaly/birth defect

f. Medical or scientific judgement should be exercised in deciding whether reporting is appropriate in other situations, such as important medical events that may not be immediately life-threatening or result in death or hospitalization but may jeopardize the subject or may require medical or surgical intervention to prevent one of the other outcomes listed in the above definition. These should also be considered serious. Examples of such events are invasive or malignant cancers, intensive treatment in an emergency room or at home for allergic bronchospasm, blood dyscrasias or convulsions that do not result in hospitalization, or development of drug dependency or drug abuse.

Clinical Laboratory Abnormalities and Other Abnormal Assessments as AEs and SAEs

Abnormal assessments (e.g., ECGs, X-rays, and vital signs) that are judged by the investigator as clinically significant will be recorded as AEs or SAEs if they meet the definition of an AE or SAE. Abnormal laboratory findings < Grade 3 (per CTCAE version 4) will only be recorded if

deemed clinically significant by the investigator. Clinically significant abnormal laboratory findings or other abnormal assessments present at baseline which significantly worsen following the start of the study will be reported as AEs or SAEs. However, clinically significant abnormal laboratory findings or other abnormal assessments that are associated with the disease being studied, unless judged by the investigator as more severe than expected for the subject's condition, or that are present or detected at the start of the study and do not worsen, will not be reported as AEs or SAEs.

The investigator will exercise his or her medical and scientific judgment in deciding whether an abnormal laboratory finding or other abnormal assessment is clinically significant.

Time Period, and Frequency of Detecting AEs and SAEs

From the time a subject consents to participate in the study until he or she has completed the study (including any follow-up period), all SAEs assessed as related to study participation (e.g., protocol-mandated procedures, invasive tests, or change in existing therapy) or related to a study concomitant medication, will be reported promptly to DSMB and the IRB

Prompt Reporting of SAEs

The investigator, or responsible person according to local requirements, will comply with the applicable local regulatory requirements related to the reporting of SAEs to regulatory authorities and the Institutional Review Board (IRB)/Independent Ethics Committee (IEC).

In addition, SAEs, whether regarded as study drug-related or not, will be reported promptly to DSMB and the IRB once the investigator determines that the event meets the protocol definition of an SAE.

Timeframes for Submitting SAE Reports to the DSMB and the IRB

Once the investigator becomes aware that an SAE has occurred in a study patient, she/he will report the information to the DSMB and IRN within 24 hours. Facsimile transmission of the SAE report is the preferred method to transmit this information. The SAE report will be completed as thoroughly as possible with all available details of the event, signed by the investigator (or designee), and forwarded within 24 hours of knowledge of the event. If the investigator does not have all information regarding an SAE, he/she will not wait to receive additional information before notifying the DSMB and IRB of the event. The report will be updated and sent to the DSMB and the IRB when additional information is received. The investigator will provide an assessment of causality at the time of the initial report.

8.0 DATA ANALYSIS AND STATISTICAL METHOD

8.1 Sample Size Determination

The study will employ a Simon 2-stage optimal design with the following specifications: $p_0 = 0.05$, $p_1 = 0.20$, $\alpha = 0.10$, $\beta = 0.10$, where p_0 is the ineffective response rate, p_1 is the effective response rate, α is the false positive rate, and β is the false negative rate. With these specifications, a 2-stage Simon optimal design, which minimizes the expected sample size given an ineffective response rate, will enroll a total of 37 patients with 12 during stage 1 and 25 during stage 2. If there is no response among the first 12 patients, then the drug is considered ineffective and the enrollment will be stopped. Otherwise, the study will proceed to stage 2. The drug will be considered effective if there are at least 4 responses by the completion of the trial.

The design will assure good statistical power with respect to differentiating response rates of 5% and 20% (12). Three additional patients will be enrolled to allow for dropouts to a total of 40.

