1.0 BACKGROUND INFORMATION AND RATIONALE FOR STUDY

1.1 Introduction

Metastatic malignant melanoma remains a disease with a very poor prognosis and median survival duration of less than one year. Durable remissions with conventional therapy are rare and therefore clinical trials remain a primary treatment modality for metastatic disease. There are 2 currently FDA-approved therapies for metastatic melanoma. Chemotherapy with single agent parenteral dacarbazine or its oral pro-drug, temozolomide, are capable of producing responses in 6.5 to 20% of patients. These responses are usually minor to partial at best and are not durable (1). Combination with other chemotherapeutic drugs has not been successful (2). The immune system also seems to play a role in malignant melanoma. High dose Interferon therapy is the current standard therapy for the adjuvant treatment of stage IIB, IIC and III melanoma after surgical resection in which it has shown to result in modest improvements in DFS and OS (3). In metastatic disease, various immunologic approaches have been utilized as well. High dose IL-2 can produce a response rate of about 10-15% in patients with metastatic melanoma. About 5-10% of responses are complete and some of these complete responses are durable so that the lucky few patients who have a durable complete response are for all intents and purposes cured (4). Attempts to combine chemotherapy with immunotherapy, so called biochemotherapy, although improving response rates, has not impacted survival as summarized in recent meta-analysis (5).

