1.3 Study Synopsis

We propose a simple phase II trial of High Dose IL-2 followed by low dose temozolomide. The study would be a preliminary phase II efficacy trial and will be conducted using a modified Simon 2 stage design in up to 40 patients total. The historic overall response rate of high dose IL-2 in melanoma is about 5-10% with CR rate about 2.5 to 5%. The response to temozolomide alone is about 13% with CR rate of about 0%. We would hypothesize that the new combination therapy would increase response rate and CR rate by at least 2 fold compared to IL-2 alone based on our retrospective experience (7). Patients with metastatic melanoma who are considered good candidates i.e. ECOG <2, Creat<2.0 Bilirubin< 2.0 for a trial of high dose IL-2 would be offered participation. Patients with a history or clinical evidence of brain metastasis must have completed radiation therapy or surgical treatment of brain lesions and have no evidence of CNS

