or MR) then accrual of an additional 25 patients will ensue. Three additional patients would be allowed to accrue to cover any early drop-outs (receipt of less than 2 complete cycles of treatment). Eligible patients would have baseline imaging with CT or CT/PET. A head MRI to rule out asymptomatic occult brain metastases will be performed on all patients as well. Patients with known brain metastases will have baseline MRI done as well and would then have follow-up MRIs performed after each course. An echocardiogram to check cardiac function and PFTs with DLCO will be performed in all patients to assure that they have adequate cardiopulmonary reserve to sustain HD IL-2 as is standard. Patients would have baseline laboratory testing done pre-treatment and at every cycle initiation. An autoimmune panel will be performed pre-treatment and after every cycle of treatment. Correlative science immunoassays will be performed pre-treatment and after every cycle of treatment. Response as per radiologic imaging assessment and physical assessment of accessible and measurable skin metastases if applicable will be performed after every course of treatment (2 cycles HD IL-2 and 21 days of temozolomide.). Response will be determined after course 1 of treatment as a complete response (CR), partial response (PR), minor response (MR), stable disease (SD) or progressive disease (PD) according to standard definitions of response. Patients with CR will receive another complete course of treatment and will then go off study except for follow-up. Patients with progressive disease (PD) will go off study after course 1. Patients with stable disease (SD) after course one will repeat one additional course maximum. Patients with PR or MR will continue with additional courses as determined by response up to a maximum of 4 courses total (8 cycles). Responses and their durability will be compared to known rates of response and their durability using HD IL-2 alone. For a population of 40, using standard HD IL-2, the expected response rate 10% would be in 4 of the 40 and the CR rate 5% in about 2 of the 40. We would hypothesize that we can at least double these at a minimum using the methods described in this protocol.

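### The Section 8.1 success count of 4 rejects a 5% response rate, but it equals the count Section 3.0 expects from IL-2 alone at 10%, so the label *effective* does not answer the comparison Section 3.0 plans

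*Combined protocol and SAP*

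**What the plan says.** Section 8.1 sets p0 = 0.05 (the ineffective rate), p1 = 0.20, α = 0.10 and β = 0.10. It enrols 12 patients and then 25, and stops after stage 1 if there are no responses. The final rule reads: "The drug will be considered effective if there are at least 4 responses by the completion of the trial". The same section adds that the design has good power to tell 5% from 20%. It gives no source or reason for 5%.

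The protocol gives three figures for IL-2 alone:

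- Section 1.1: "High dose IL-2 can produce a response rate of about 10-15% in patients with metastatic melanoma".
- Section 1.3: "The historic overall response rate of high dose IL-2 in melanoma is about 5-10% with CR rate about 2.5 to 5" (percent). It then hypothesizes that the combination "would increase response rate and CR rate by at least 2 fold compared to IL-2 alone".
- Section 3.0: for 40 patients on standard IL-2, "the expected response rate 10% would be in 4 of the 40 and the CR rate 5% in about 2 of the 40". It continues: "We would hypothesize that we can at least double these at a minimum using the methods described in this protocol".

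Section 3.0 also commits to the comparison: "Responses and their durability will be compared to known rates of response and their durability using HD IL-2 alone". It names no criterion for it. Section 8.2 counts only PR and CR as responses in the final analysis and plans a 95% confidence interval for the response rate, but ties that interval to no decision.

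**The concern.** The rule in 8.1 and the comparison in 3.0 use different reference rates. The rule is calibrated against 5%, while 3.0 measures the regimen against 10%, and 10% is the only value common to all three IL-2 statements. The alternative of 20% is double that 10%, so p0 and p1 appear to rest on different baselines.

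At stake is what a result of 4 of 37 would be taken to mean. Section 3.0 promises a comparison with IL-2 and gives no criterion of its own. The only decision rule in the plan is the one in 8.1. A regimen that added nothing to IL-2 at the protocol's own 10% could then be labelled effective, and the label read as support for the doubling hypothesis.

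**Working it through.** **Inputs.** From 8.1: n1 = 12, n2 = 25, stop at 0 of 12, success at 4 or more of 37, p0 = 0.05, p1 = 0.20, α = β = 0.10. Benchmarks for IL-2 alone: 5–10% (1.3), 10% (3.0), 10–15% (1.1). A response is PR or CR (8.2), here applied at both stages.

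**Formula.** With X1 ~ Bin(12, p) and X2 ~ Bin(25, p) independent,

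P(effective) = P(X1 ≥ 1 and X1 + X2 ≥ 4) = Σ over x from 1 to 3 of P(X1 = x)·P(X2 ≥ 4 − x), plus P(X1 ≥ 4).

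**Step 1: reproduce the plan's design.**

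At p = 0.05: 0.3413 × 0.1271 + 0.0988 × 0.3576 + 0.0173 × 0.7226 + 0.0022 = 0.0434 + 0.0353 + 0.0125 + 0.0022 = 0.093 (limit 0.10).

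At p = 0.20 the same sum is 0.902 (target 0.90).

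The probability of stopping early at 5% is 0.95^12 = 0.540, so the expected sample size is 12 + 25 × 0.460 = 23.5. An exhaustive search for the smallest expected sample size at 5% returns exactly 12 + 25, stop at 0, success at 4 or more. Section 8.1 is correct for the question it sets.

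**Step 2: expected count with no improvement.** At 10%, 0.10 × 37 = 3.7 and 0.10 × 40 = 4.0. The success count is 4.

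**Step 3: the same rule at the protocol's IL-2 rates.**

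At p = 0.10: 0.3766 × 0.4629 + 0.2301 × 0.7288 + 0.0852 × 0.9282 + 0.0256 = 0.1743 + 0.1677 + 0.0791 + 0.0256 = 0.447.

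| True response rate | P(effective) |
|---|---|
| 5% (low end of 1.3) | 9.3% |
| 7.5% (midpoint of 1.3) | 25.6% |
| 10% (3.0; top of 1.3; bottom of 1.1) | 44.7% |
| 15% (top of 1.1) | 75.1% |
| 20% (p1) | 90.2% |

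**Step 4: what the minimum success result shows.** 4/37 = 10.8%. Section 8.2 names no interval method. The exact (Clopper–Pearson) 95% CI, taking n = 37 as fixed, is 3.0% to 25.4%, which contains 5%, 10%, 15% and 20%.

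**Step 5: what 12 + 25 patients could show against 10%, for scale.** Keeping the stop at 0 of 12:

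| Final count | Chance at a true 10% | Chance at a true 20% |
|---|---|---|
| 6 or more | 15.0% | 75.1% |
| 7 or more | 6.8% | 61.5% |
| 9 or more | 0.9% | 31.1% |

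Seven is the smallest count that holds the one-sided 10% level against 10%. Nine is the smallest count whose exact 95% CI lies wholly above 10% (lower limit 11.8% at 9/37; 9.8% at 8/37).

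**The case against.** The strongest defence is that 8.1 already says what it tests. It calls p0 the ineffective rate, not the IL-2 rate, says the design separates 5% from 20%, and claims no superiority over IL-2. Section 8.2 supplies a confidence interval, and the trial is described as preliminary. All of that stands. A reader might infer that the Simon calculation is wrong. It is not: the design reproduces exactly.

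A reader might also infer that meeting the rule can never support a comparison with IL-2. The documents do not support that either. Section 1.3 allows an IL-2 rate as low as 5%, and against 5% the error is 9.3%. Nor does 1.3 plan the comparison. It states a hypothesis, and only 3.0 says the comparison will be made.

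A benchmark below 10% may also be defensible, because inclusion criterion 7 admits patients with prior IL-2 or temozolomide and the quoted rates may not apply to them. But the protocol does not make this argument, does not state the share of such patients, and in 3.0 applies 10% to its own 40.

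Finally, quoting only the 31.1% from step 5 would undersell the design, since a 95% CI wholly above 10% is a stricter demand than the plan's one-sided 10% level. At that level, 7 of 37 has 61.5% power at 20%.

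What remains is that neither 3.0 nor 8.1 says the label does not answer the comparison 3.0 plans.

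**Conclusion.** The concern holds for the benchmarks in 3.0 and 1.1, not for the low end of 1.3. The rule in 8.1 is sound for 5% versus 20%. Read against the 10% that 3.0 expects from IL-2 alone, it would declare a regimen with no improvement effective 44.7% of the time, and 75.1% at the 15% in 1.1, against a planned false-positive rate of 10%.

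Assumptions: 37 evaluable patients; PR and CR counted at both stages; exact intervals that ignore the two-stage sampling. With 40 evaluable patients and the same cut-off, the figure at 10% is 49.1%, so the conclusion does not depend on the denominator. Section 3.0 also lets minor responses open stage 2. That is a separate inconsistency and is not needed for this point.

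This should be fixed before results are known, because it changes what the trial may conclude from 4 of 37.

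**What to change.** Keep 12 + 25 patients and the 4-response rule.

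1. Reconcile the IL-2 response rates in 1.1, 1.3 and 3.0. In 8.1, tie p0 to the reconciled rate, or say why 5% applies (for example, to the pretreated patients admitted by inclusion criterion 7).
2. State in 3.0 and 8.1 that 4 or more PR/CR among 37 rejects only a 5% rate at the one-sided 10% level, has about a 45% chance of occurring at a true rate of 10%, and will not be reported as improvement over IL-2 alone. State that the comparison in 3.0 will rest on the response rate and its 95% CI, name the CI method, and give the interval at the minimum success result (exact: 3.0% to 25.4%).

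The cost is wording only, with no added patients and no change to the decision rule. The downside is that the trial's stated ability to support a claim over IL-2 becomes less favourable, as step 5 shows. The counts of 7 and 9 there illustrate that limit and are not proposed as a second success threshold.
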